10.1. Adverse Events

All reported AEs will be coded using the MedDRA coding dictionary version 24.0 or later, and summarized by System Organ Class (SOC) and Preferred Term (PT),.

Refer to the Core SAP for AE start date imputation, AE counting rules, definition of AEs related to study drug, definition of AEs of special interest, and TLF contents.

Tables present number and percentage of subjects experiencing AEs by SOC and PT, unless specified otherwise. AEs are tabulated in descending order of overall frequency within SOC and PT.

A by-subject listing of AEs is provided for the enrolled analysis set.

10.1.1. Deaths

Deaths are identified from the following sources:

- AE CRF: PT or reported term containing "death," outcome of fatal, yes" response to any death-related question (e.g., "Did the AE result in death?"; "Is a death certificate available?"; "Is an autopsy report available?"); or non-missing death date.
- Subject Disposition CRF: study non-completion reason of death.

A by-subject listing of deaths is provided for the enrolled analysis set.

10.1.2. AE Overview

An AE overview without SOC and PT presents the number and percentage of subjects with any of the following AEs: any AE, mild AE, moderate AE, severe AE, moderate or severe AE, AE related to study drug, AE leading to study drug discontinuation, SAE, SAE related to study drug, SAE leading to study drug discontinuation, potential drug abuse AE, hepatic-related AE, cardiovascular AE, and suicidality AE.

An AE overview is produced for each analysis period (pre-treatment, on-treatment) for the safety analysis set.

10.1.3. On-treatment AEs

On-treatment AEs are tabulated for the safety analysis set by SOC and PT for the following endpoints:

- AEs by intensity (total, mild, moderate, severe, moderate or severe, not reported)
- AEs related to study drug by intensity

This document is confidential.

- AEs by relationship to study drug (related, possibly related, unlikely related, not related, not reported)
- SAEs
- AEs leading to study drug discontinuation

10.1.4. *Follow-up AEs*

Follow-up AEs are tabulated for the safety analysis set by SOC and PT for the following endpoints:

- AEs by intensity (total, mild, moderate, severe, moderate or severe, not reported)
- SAEs

10.2. **Laboratory Evaluations**

Laboratory parameters include, but are not limited to, assessments in Table 3.

Table 3. Laboratory Parameters

Hematology	Serum Chemistry	Urinalysis
Full and differential blood count	albumin	appearance
Hct	ALT	pH
Hb	ALP	protein
MCH	AST	glucose
MCHC	BUN or urea	ketone bodies
MCV	carbon dioxide	specific gravity
Platelet count	creatinine	urobilinogen
RBC count	eGFR	bilirubin
WBC count with differential	creatine phosphokinase	occult blood
	electrolytes (sodium, potassium, chloride, calcium, phosphorus)	nitrates
	GGT	leukocytes
	glucose	
	LDH	
	total bilirubin	
	direct and indirect bilirubin	
	total cholesterol	
	LDL	
	HDL	
	triglycerides	
Pregnancy test: A human chorionic gonadotropin (hCG) blood test will be conducted on all WOCBP at screening; an hCG urine test will be conducted at all subsequent visits according to Error! Reference source not found..		
Urine drug screen: Drugs of abuse include, but are not limited to, amphetamines, barbiturates, benzodiazepines, tetrahydrocannabinol, cocaine, opiates, and PCP (see Error! Reference source not found. Assessments). Retesting for positive results that are exclusionary is not allowed.		
Sputum test: Refer to Section Error! Reference source not found. of protocol.		

Abbreviations: ALP=alkaline phosphatase; ALT=alanine aminotransferase; AST=aspartate aminotransferase; BUN=blood urea nitrogen; eGFR=estimated glomerular filtration rate; GGT=gamma-glutamyl transpeptidase; Hb=hemoglobin; HBV=hepatitis B; Hct= hematocrit; HDL=high-density

This document is confidential.

lipoproteins; LDH=lactate dehydrogenase; LDL=low-density lipoproteins; MCH=mean corpuscular hemoglobin; MCHC=mean corpuscular hemoglobin concentration; MCV=mean corpuscular volume; PCP=phencyclidine; pH=potential hydrogen; RBC=red blood cell; WBC=white blood cell; WOCBP=women of childbearing potential.

Blood and urine samples will be analyzed at a central laboratory facility. Each subject will be assessed with the following laboratory tests and parameters:

- Clinical laboratory samples will be collected Visit 1, Visit 5, Visit 8, and at Follow-Up.
- Urinalysis samples will be collected at Visit 1, Visit 5, and Visit 8.
- A serum pregnancy test will be conducted at Screening and urine pregnancy testing at Visit 5 and Visit 8.
- Urine drug testing will be performed at Visit 1 only.

Urine samples will be analyzed by dipstick, and a microscopic analysis will be performed if the results of dipstick indicate abnormalities to be further investigated.

TLFs show data in the Systeme Internationale (SI) unit system, if applicable. Tables present results by treatment group and overall, and laboratory tests alphabetically within laboratory test group, as applicable.

Clinically significant laboratory test abnormalities will be identified as Grade 3 to Grade 4 laboratory test results graded accordingly to numeric laboratory test criteria in Common Terminology Criteria for Adverse Events (CTCAE) version 5.0 (2017), if available. Otherwise, if CTCAE grades are not available, then results will be graded according to numeric laboratory test criteria in Division of AIDS (DAIDS) Table for Grading the Severity of Adult and Pediatric AEs. If a subject has a laboratory test abnormality with different toxicity grades over time, then only the highest toxicity grade will be reported in the lab abnormality summary table. Refer to the Core SAP for laboratory tests of clinical interest for analyses, including identification of those with toxicity grades.

10.2.1. *Laboratory Test Abnormalities*

On-treatment laboratory test abnormalities are tabulated as the number and percentage of subjects in the safety analysis set in the following tables:

- Worst (highest) on-treatment laboratory test abnormality for each graded laboratory test.
- Laboratory test toxicity grade shift from baseline to the worst on-treatment toxicity grade for each graded laboratory test.

Refer to the Core SAP for toxicity grade categories and additional details.

10.2.2. *Liver Function Test Elevations*

Refer to the Zavegeptan Core SAP for LFT elevation categories and additional details.

LFT Elevations: Cumulative, Mutually Exclusive, and Composite

LFT elevations are based on fold changes above ULN. The number and percentage of subjects with prespecified LFT elevations are tabulated separately for each analysis period (pre-treatment, on-treatment) for the safety analysis set.

LFT ULN Shifts from Baseline to Worst Elevation

This document is confidential.

LFT ULN shifts from baseline to the worst (highest) on-treatment LFT elevation are tabulated as the number and percentage of subjects in the safety analysis set in pre-specified elevation categories.

LFT Plots

An evaluation of drug-induced serious hepatotoxicity (eDISH) scatter plot displays the maximum TBL ratio of value to ULN on the y-axis versus the maximum ALT ratio of value to ULN on the x-axis by treatment group, where both maxima are on treatment but not necessarily concurrent.

10.2.3. *Laboratory Test Changes from Baseline*

Values and changes from baseline in hematology and serum chemistry laboratory tests are tabulated descriptively as continuous variables at baseline and each scheduled visit in the on-treatment and follow-up analysis periods.

10.2.4. *Laboratory Test Listings*

All laboratory test listings will be based on the enrolled analysis set.

A by-subject listing of the following select laboratory tests is provided for subjects with at least one laboratory assessment of grade 3 or 4 abnormality or a positive pregnancy test result: hematology results, serum chemistry results, and urinalysis results. If there is a positive pregnancy test, defined as a serum or urine pregnancy test with either (1) “positive” character value, or (2) numeric value ≥ 25 U/L. the listing will also include all pregnancy test results over time.

Refer to Section 6.4.2.6 of the Core SAP for listing contents as applicable to this study.

A by-subject listing displays all LFT results over time for subjects with select LFT elevations (ALT or AST $> 3x$ ULN; ALP or TBL $> 2x$ ULN) at any time point. Refer to Section 6.4.2.6 of the Core SAP for listing contents as applicable to this study.

10.3. *Vital Signs and Physical Measurements*

Vital signs will be taken at Visit 1, Visit 5, Visit 6, Visit 7, and Visit 8.

The vital signs to be captured are systolic blood pressure, diastolic blood pressure, heart rate, respiratory rate, and temperature. Temperature will be presented in summaries and listings in Celsius (Temperature (in °C) = 5/9 (Temperature [in °F]-32)).

10.3.1. *Vital Sign and Physical Measurement Change from Baseline*

Values and changes from baseline in vital signs and physical measurements will be tabulated descriptively as continuous variables at baseline and each scheduled visit in the on-treatment analysis period.

10.3.2. *Vital Sign and Physical Measurement Abnormalities*

On-treatment vital sign and physical measurement abnormalities are tabulated as the number and percentage of subjects in the safety analysis set in categories specified in the Core SAP.

10.4. *Spirometry*

Spirometry will be measured at every visit during Part 1 (Screening) and after each study dose treatment at Visits 5 through 8. Spirometry is used to monitor baseline lung function and gauge the level of bronchoconstriction during methacholine and allergen challenges. Measurements include: forced vital capacity (FVC) in liters, FEV1 in liters, and the percentage of predicted FEV1 value. Results are tabulated

This document is confidential.

pre-treatment and on-treatment for the safety analysis set. On-treatment data will also include changes from baseline.

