6.2.2 Secondary Endpoints

- Allergen-induced EAR assessed as maximum percentage decrease in FEV₁ between 0 and 2 hours after the administration of the allergen inhalation challenge.
- Allergen-induced change in AHR (methacholine PC₂₀) at 24 hours post-allergen challenge.

- Safety and tolerability of oral zavegeptan assessed using the frequency of TEAEs and serious TEAEs through end of study, and clinically significant laboratory abnormalities.

CCI

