15.3 Safety Analysis

All reported AEs will be coded using the Medical Dictionary for Regulatory Activities (MedDRA) latest version available at start of the study. The incidence of treatment-emergent

AEs (TEAEs; events with onset dates on or after the start of the study drug) will be included in incidence tables. Events with missing onset dates will be included as treatment-emergent. If a subject experiences more than 1 occurrence of the same AE, the occurrence with the greatest severity and the closest association with the study drug will be used in the summary tables. Treatment-related AEs, SAEs and AEs causing discontinuation will be tabulated. All AEs will be listed by subject, along with information regarding onset, duration, relationship and severity to study drug, action taken with study drug, treatment of event, and outcome.

Clinically significant laboratory test abnormalities will be identified as Grade 3 to 4 laboratory test results graded according to numeric laboratory test criteria in Common Terminology Criteria for Adverse Events (CTCAE) version 5.0 (2017), if available. Otherwise, if CTCAE grades are not available, then results will be graded according to numeric laboratory test criteria in Division of Aids (DAIDS) Table for Grading the Severity of Adult and Pediatric AEs. If a participant has a laboratory test abnormality with different toxicity grades over time, then only the highest toxicity grade will be reported in the lab abnormality summary table.

Clinical laboratory data and vital signs will be summarized using descriptive statistics, including mean values and mean change from baseline values, as well as numbers of subjects with values outside limits of the normal range at each time point.

Summary tables will be provided for concomitant medications initiated during the study period.

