11.2. Analysis Periods

Analysis periods are defined as follows:

- Pre-treatment: measurement date/time on or before the study drug start date. This period is used to derive baseline values and to assess safety endpoints. Note that all measurements are pre-treatment for subjects in the enrolled analysis set with missing study drug start date. Note that AEs with imputed start date equal to the study drug start date are NOT part of this period.
 - Pre-treatment will include Visits 1 – 5 / Study Days -29 – 1
- On-treatment: measurement date/time after the study drug start date through the study drug last date + 7 days or ending at the follow-up visit, whichever is earliest. This period is used to assess safety endpoints on treatment. Note that AEs with imputed start date equal to the study drug start date are part of this period.

This document is confidential.

- On-treatment will include Visits 6 – 8 / Study Days 1 – 28
- Follow-up: measurement date after the study drug last date + 7 days or starting at the follow-up visit, whichever is earliest. This period is used to assess safety endpoints during follow-up.
 - Follow-up will include Visit 9 / Study Days 35 – 41

See [Section 11.1](#) for derived dates for determining analysis periods. If measurement time is missing, not collected, or not applicable for a parameter, then the measurement date is compared to the derived date.

This document is confidential.

12. Interim Analyses

No interim analyses are planned for this study.

This document is confidential.

SAP text Version: SAP text version 2.0 24-May-2023

Filing requirements: TMF

Page 36 of 42

13. Changes from Analysis Planned in Protocol

The Treated Population is defined in the study protocol. However, it has been renamed the Safety Population in the SAP.

One additional study populations were added that are not defined in the study protocol, the Follow-up population.

This document is confidential.

14. Quality Control

SAS programs are developed to produce output such as analysis data sets, summary tables, data listings, figures or statistical analyses. An overview of the development of programs is detailed in Syneos Health Developing Statistical Programs SOP (3907) .

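### The summary tables of graded lab and liver-test abnormalities, and the eDISH plot, omit Visit 9, one of two scheduled post-dose draws, and no table counts distinct subjects with a TEAE through end of study

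*SAP*

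**What the plan says.** **Endpoint.** Protocol 6.2.2 has safety and tolerability "assessed using the frequency of TEAEs and serious TEAEs through end of study, and clinically significant laboratory abnormalities". Protocol 15.3 defines TEAEs as "events with onset dates on or after the start of the study drug", with no upper limit. It takes clinically significant lab abnormalities to be Grade 3 to 4 results, reports the highest grade a participant reaches over time, and calls for treatment-related AEs to be tabulated. The safety estimand in SAP 4.2 is a frequency by treatment group, with no period stated.

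**Periods.** SAP 11.2 runs on-treatment from after the study drug start date "through the study drug last date + 7 days or ending at the follow-up visit, whichever is earliest". It states that Visit 9 belongs to follow-up.

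**Lab summaries.** SAP 10.2.1 plans the "Worst (highest) on-treatment laboratory test abnormality for each graded laboratory test" and a grade shift to the worst on-treatment grade. In SAP 10.2.2, LFT elevations are tabulated for pre-treatment and on-treatment, "LFT ULN shifts from baseline to the worst (highest) on-treatment LFT elevation are tabulated", and the eDISH plot uses on-treatment maxima.

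**Adverse events.** SAP 10.1.2: "An AE overview is produced for each analysis period (pre-treatment, on-treatment) for the safety analysis set". SAP 10.1.4: "Follow-up AEs are tabulated for the safety analysis set by SOC and PT for the following endpoints"; those endpoints are AEs by intensity and SAEs.

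**The concern.** The protocol's lab component is a frequency of Grade 3-4 results with no on-treatment limit. The SAP outputs that would deliver that frequency by arm close before the last scheduled blood draw. A liver enzyme or bilirubin rise that first appears or peaks 7 to 10 days after the last dose would not enter the abnormality count, the LFT tables or the eDISH plot. Liver safety is a declared interest of this protocol: exclusions 6, 19 and 22 screen for it, and section 12.2.5 sets a rule for potential drug-induced liver injury.

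For adverse events the endpoint explicitly runs through end of study. The SAP reports on-treatment and follow-up separately, and a reader cannot combine the two counts without knowing who appears in both.

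**Working it through.** No stated figure needs reproducing. The check assigns each scheduled draw to an analysis period.

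**1. Draws.** SAP 10.2 schedules hematology and chemistry at Visits 1, 5, 8 and follow-up (Visit 9). Protocol 10.2.2 places the Visit 5 sample before the first dose. That leaves 4 − 2 = 2 scheduled post-dose draws: Visits 8 and 9. Urinalysis has only Visit 8 after dosing and is unaffected.

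**2. Where Visit 9 falls.** The schedule puts Visit 8 at about Day 28 (+3 days), so the last dose is about Day 28 to 31. Visit 9 is 7 to 10 days later: 28 + 7 = 35 to 31 + 10 = 41, matching the scheduled Days 35 to 41.

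| Visit 9, days after last dose | Last possible on-treatment day | Period of Visit 9 |
|---|---|---|
| +7 | +7 | boundary day; SAP 11.2 names Visit 9 as follow-up |
| +8, +9, +10 | +7 | follow-up |

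**3. Coverage by output.**

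| SAP output | Includes Visit 9? |
|---|---|
| Worst graded abnormality (10.2.1) | No |
| Toxicity-grade shift (10.2.1) | No |
| LFT elevations (10.2.2) | No |
| LFT shifts (10.2.2) | No |
| eDISH plot (10.2.2) | No |
| Values and changes from baseline (10.2.3) | Yes |
| Grade 3/4 and LFT listings (10.2.4) | Yes |

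The first five use 1 of 2 scheduled post-dose draws (50%).

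**4. Early discontinuation.** No blood draw is scheduled between Visits 5 and 8, and Protocol 8.6 asks subjects who stop early to attend Visit 9. For someone who stops before Visit 8, Visit 9 may be the only scheduled post-dose draw. That subject could contribute 0 of 1 scheduled results to the five summaries. Protocol 8.6 also asks for exit procedures at withdrawal, so whether this happens depends on how that visit is recorded.

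**5. Effect on the count.** One subject whose first Grade 3 value is at Visit 9 adds 0 to the planned count instead of 1. At the planned 12 per arm that is 1/12 = 8.3%. SAP section 2 says the study ended early for low enrollment. Arm sizes are not given; the weight of one subject is 1/n and grows as n falls.

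**6. Adverse events.** Let a subjects in an arm of n have an on-treatment AE and b a follow-up AE. The number with any TEAE through end of study lies between max(a, b) and the smaller of a + b and n. The two tables alone do not fix it. The same holds for serious TEAEs. For follow-up there is no relatedness table, and the overview rows for hepatic, cardiovascular and suicidality AEs have no follow-up counterpart.

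**The case against.** The strongest reply is that little is hidden, and most of it stands.

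- A reader might infer that every lab and liver output stops before Visit 9. The documents do not support this. The Grade 3/4 listing has no period limit, and the LFT listing is triggered by an elevation at any time. The change-from-baseline tables cover follow-up, and SAP 6.1 includes the minimum and maximum, so the highest Visit 9 ALT per arm is tabulated.
- A reader might infer that late safety events are lost. They are not. Follow-up AEs and SAEs have their own tables. Protocol 12.9 makes lab results judged clinically significant AEs, and 12.2.5 makes potential drug-induced liver injury an SAE. Follow-up SAEs also feed the narrative listing in SAP 10.6.
- A reader might infer that on-treatment stops at Visit 8 or at the last dose. It runs up to 7 days beyond the last dose, so AEs and unscheduled labs in that week count unless Visit 9 comes first.
- The end-of-study wording in Protocol 6.2.2 attaches to TEAEs. For labs the argument rests on the absence of any on-treatment limit there and in 15.3.
- SAP version 2.0 was written to reduce the number of outputs, and in a small study listings can be read by hand.
- The Core SAP and the table shells are not available. A combined TEAE row could be in them.

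Three things remain. Listings and maxima do not give the by-arm frequency that SAP 4.2 names as the summary. The on-treatment lab limit is explicit, and SAP section 2 gives this SAP primacy over the Core SAP where they differ. Protocol section 15 lets the SAP supersede it, but SAP section 13, which records changes from the protocol, does not mention this one.

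**Conclusion.** The point holds for the five lab summaries and for the missing combined TEAE count. Followed as written, the SAP can undercount the by-arm frequency of Grade 3-4 abnormalities, because it leaves out one of two scheduled post-dose hematology and chemistry draws, and possibly the only one for subjects who stop before Visit 8. Each subject missed is 8.3% of a planned arm of 12, a size the terminated study may not have reached. Whether anyone is actually missed depends on the data.

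It would go too far to say that the safety endpoint cannot be assessed from the planned outputs. The data are collected, listed and partly tabulated, and no efficacy inference is touched. For adverse events the gap is narrower: a count of distinct subjects through end of study, and relatedness for follow-up events. That part assumes the unseen Core SAP and shells do not already supply them.

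**What to change.** In SAP 10.2.1 and 10.2.2, define the window as worst post-baseline: after the first dose through end of study, including Visit 9 and unscheduled labs. Apply it to the existing graded-abnormality, grade-shift, LFT-elevation, LFT-shift and eDISH outputs. The five summaries would then cover 2 of 2 scheduled post-dose draws.

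In SAP 10.1.2, add rows to the existing AE overview for any TEAE, any serious TEAE and any related TEAE through end of study, counting each subject once.

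The cost is SAP wording, a period flag in existing programs and a few rows. It needs no new data and no new table, so it fits the aim of a shorter report. The downside is slightly more programming and summaries that mix time on and off drug. Flagging values first seen at follow-up keeps the two distinguishable.

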10.5. S-STS

The S-STS is a prospective, clinician-administered rating questionnaire with 16 patient-reported questions and 6 clinician-reported questions that tracks both treatment-emergent suicidal ideation and behaviors. The S-STS will be performed at Visit 1, Visit 5, and Visit 8.

Refer to the Core SAP for calculation of the S-STS ideation subscale, behavior subscale, and total scores.

Values and changes from baseline in the self-reported S-STS ideation subscale, behavior subscale, and total score are tabulated descriptively as continuous variables at baseline and the worst (highest) score in the analysis periods. The table also presents the number and percentage of subjects in the worst (highest) score change from baseline category (i.e., < -1, -1, no change, 1, >1) in analysis periods for the ideation subscale, behavior subscale, and total score.

Results are tabulated on-treatment for the safety analysis set.

10.6. Safety Narratives

A by-subject listing of safety narrative subject identifiers is provided for the following select events and analysis sets as columns:

- Deaths for the enrolled analysis set
- On-treatment and follow-up SAEs for the safety analysis set, regardless of relationship to study drug
- AEs leading to discontinuation of study drug across all analysis periods for the safety analysis set, regardless of relationship to study drug
- On-treatment events of special interest for the safety analysis set:
 - ALT or AST > 3x ULN
 - ALT or AST > 3x ULN concurrent with TBL > 2x ULN
 - ALP or TBL > 2x ULN
 - Select hepatic-related AEs, i.e., PTs containing cirrhosis, hepatic failure, hepatitis, jaundice, or liver failure
 - Cardiovascular AEs
 - Suicidality AEs

Refer to the Core SAP for additional details. The listing flags subjects with select events.

Should the criteria stated in the Biohaven Zavegeptan Safety Narrative Scope conflict with the criteria above, the Biohaven Zavegeptan Safety Narrative Scope will take precedence.

